3 OBJECTIVES AND ENDPOINTS

OBJECTIVES	ENDPOINTS	JUSTIFICATION FOR ENDPOINTS	PUTATIVE MECHANISMS OF ACTION
Primary			
To test initial efficacy of intensive ASSIST	(1) Perceptual accuracy of treated targets 1 week post treatment (2) Perceptual accuracy of full set of targets 1 week post treatment Greater change score in the ASSIST group than in the no-ASSIST group at T2 (t-test, $\alpha=.05$, 2-tailed)	Perceptual accuracy reflects speech motor planning skills, the presumed underlying impairment in CAS.	ASSIST targets speech motor planning skills, which is expected to improve perceptual accuracy of speech.
Secondary			
To optimize ASSIST: To compare Simple vs. Complex practice	(1) Perceptual accuracy of treated targets 1 week post treatment (2) Perceptual accuracy of full set of targets 1 week post treatment Greater change score in the Simple or Complex ASSIST group pre to post (t-test, $\alpha=.05$, 2-tailed)	Perceptual accuracy reflects speech motor planning skills, the presumed underlying impairment in CAS.	Simple practice establishes building blocks, fosters success Complex practice provides more practice integrating and sequencing movements

OBJECTIVES	ENDPOINTS	JUSTIFICATION FOR ENDPOINTS	PUTATIVE MECHANISMS OF ACTION
To optimize ASSIST: To compare Word vs. Nonword targets	(1) Perceptual accuracy of treated targets 1 week post treatment (2) Perceptual accuracy of full set of targets 1 week post treatment Greater change score in the Word or Nonword ASSIST group pre to post (t-test, $\alpha=.05$, 2-tailed)	Perceptual accuracy reflects speech motor planning skills, the presumed underlying impairment in CAS.	Word targets enhance learning via increased motivation due to functional relevance and practice outside treatment Nonword targets enhance learning through focus on underlying speech motor skill of assembling motor plans (vs. retrieving existing speech motor plans)
To optimize ASSIST: To compare Massed vs. Distributed practice	(1) Perceptual accuracy of treated targets 1 week post treatment (2) Perceptual accuracy of full set of targets 1 week post treatment Greater change score in the Massed or Distributed ASSIST group at T3 (t-test, $\alpha=.05$, 2-tailed)	Perceptual accuracy reflects speech motor planning skills, the presumed underlying impairment in CAS.	Massed practice facilitates neuroplasticity (reported to be optimal in neuroplasticity literature and the few studies with CAS and other pediatric speech sound disorders) Distributed practice results in more forgetting, and requires deeper processing for the next attempt (reconstructing the movement from scratch), resulting in more detailed movement plans
To determine effects of ASSIST on distal outcome measures	ICS Greater change score in the ASSIST group than in the no-ASSIST group at T2 (t-test, $\alpha=.05$, 2-tailed)	ICS reflects caregiver-reported perception of the effectiveness of everyday speech communication of their child.	Improved speech motor planning skills lead to increased speech accuracy, which increases intelligibility in everyday contexts.
To determine effects of ASSIST on distal outcome measures	FOCUS-34 Greater change score in the ASSIST group than in the no-ASSIST group at T2 (t-test, $\alpha=.05$, 2-tailed)	FOCUS reflects caregiver-reported perception of the communicative function of their child in everyday life.	Increased speech accuracy and intelligibility facilitates everyday communication interactions and communicative confidence.
To determine effects of ASSIST on distal outcome measures	TOCS+ Intelligibility Greater change score in the ASSIST group than in the no-ASSIST group at T2 (t-test, $\alpha=.05$, 2-tailed)	TOCS+ reflects gold-standard measure of speech intelligibility	Improved speech motor planning skills lead to increased speech accuracy, which increases intelligibility.
Tertiary/Exploratory			
To evaluate safety of ASSIST	Clinician-rated child frustration level (FRS)	FRS: Acts as a safety mechanism, to avoid unnecessary treatment-related frustration (stopping rule based on FRS)	Intensive speech therapy, with many repeated failures and corrective feedback, could increase child frustration levels.

4 STUDY DESIGN

4.1 OVERALL DESIGN

4.1.1 OVERVIEW

Below is a reminder of the design of the four RCTs in this study (3 cycles plus 1 study combined across Cycles 1 and 2). Dashed box indicates the primary study (Study 1: ASSIST vs. Delayed Control).

Cycle 1 (Summer 1): COMPLEXITY (simple vs. complex real words).								
Group	Condition	wk1	wk2	wk3	wk4	wk5	wk6	wk7
Immediate ASSIST	Simple	T1	8 hrs	8 hrs	T2			T3
	Complex		8 hrs	8 hrs				
Delayed ASSIST	Simple					8 hrs	8 hrs	
	Complex					8 hrs	8 hrs	

Cycle 2 (Summer 2): LEXICALITY (words vs. nonwords).								
Group	Condition	wk1	wk2	wk3	wk4	wk5	wk6	wk7
Immediate ASSIST	Real	T1	8 hrs	8 hrs	T2			T3
	Nonsense		8 hrs	8 hrs				
Delayed ASSIST	Real					8 hrs	8 hrs	
	Nonsense					8 hrs	8 hrs	

Cycle 3 (Summer 3): INTENSITY (massed vs. distributed treatment).								
Group	Condition	wk1	wk2	wk3	wk4	wk5	wk6	wk7
Massed ASSIST	Immediate	T1	8 hrs	8 hrs	T2			T3
	Delayed					8 hrs	8 hrs	
Distributed ASSIST	Distributed		4 hrs	4hrs		4 hrs	4 hrs	

Given the interwoven design (see **Section 1.2, Schema**, figure repeated above), in both Cycles 1 and 2, children are allocated with equal probability to one of four groups (Immediate Simple/Word, Immediate Complex/Nonword, Delayed Simple/Word, Delayed Complex/Nonword) (5:5:5:5). In Cycle 3, children are allocated to one of 3 groups (Distributed vs. Massed Immediate vs. Massed Delayed) to such that children have equal probability to receive Massed or Distributed ASSIST (5:5:10).

4.1.2 COMMON ELEMENTS

4.1.2.1 RANDOMIZATION

Randomization is determined by an investigator not involved in assessment or intervention (biostatistician). Children are randomly allocated to conditions via permuted block randomization (block

size 4) within each recruitment cycle, to maximize equivalent group sizes across phases and conditions. The biostatistician sends the randomization sequence (a series of letters ABCD in random order) to a research assistant not otherwise involved in the study, who assigns a particular phase (Immediate or Delayed) + condition (Simple/Complex, Word/Nonword) combination to each letter and creates serially numbered sealed opaque envelopes with the randomization sequence. Group assignment is concealed from any personnel involved in child and caregiver interactions until after assessment and target selection is complete. Allocation is revealed for all children in a lab meeting with at least three team members present to avoid errors.

4.1.2.2 INTERVENTION

All children receive 16 hours (32 sessions of 30 minutes) of ASSIST, across 4 sessions per day, 4 days per week for 2 weeks (either the first two weeks or the second two weeks). All children are tested 1 week before treatment (T1), after 2 weeks (T2), and post treatment (T3). The critical comparison is at T2 for Study 1 (ASSIST vs. No ASSIST), at T3 for Study 4 (Massed vs. Distributed ASSIST), and post treatment (T2 or T3) for Studies 2 and 3 (Simple vs. Complex and Word vs. Nonword ASSIST).

ASSIST (Apraxia of Speech Systematic Integral Stimulation Treatment) is a theoretically grounded and clinically informed speech therapy intervention for CAS. ASSIST involves repeated structured practice of meaningful words and phrases with cueing and feedback. It incorporates principles of motor learning and systematically adapts difficulty and introduces new targets based on a child's performance. Targets are embedded in carrier phrases (frames).

4.1.3 STUDY-SPECIFIC HYPOTHESES AND ENDPOINTS

4.1.3.1 STUDY 1: ASSIST VS. NO (DELAYED) ASSIST

Study 1 is a single-site Phase 1 randomized clinical trial using a prospective outcome-assessor-blinded two-arm delayed control group (cross-over) design. The critical outcome assessment point is 1-week post treatment for the Immediate ASSIST group (T2).

ASSIST Hypothesis: ASSIST improves speech motor planning skills in CAS. This hypothesis predicts a greater increase in perceptual speech accuracy at 1 week post treatment for children who receive ASSIST than children who do not receive ASSIST.

4.1.3.2 STUDY 2: SIMPLE ASSIST VS. COMPLEX ASSIST

Study 2 is a single-site Phase 1 randomized clinical trial using a prospective outcome-assessor-blinded two-arm group design. The critical outcome assessment point is 1-week post treatment (either T2 or T3, depending on the Immediate or Delayed allocation).

Simple ASSIST involves ASSIST (see above) in which the frames (carrier phrases) are simple, as defined by an Index of Phonetic Complexity (IPC) value of 0-2. Complex ASSIST involves ASSIST in which the frames are complex, as defined by an IPC value of 3-5.

Simplicity Hypothesis: Children with CAS learn more effectively with simple targets. Simpler sounds and syllables foster early success and enable the child to build longer, more complex movement plans by combining basic building blocks. This hypothesis predicts a greater increase in perceptual speech accuracy at 1 week post treatment for children who receive Simple ASSIST than children who receive Complex ASSIST.

Complexity Hypothesis: Children with CAS learn more effectively with complex targets. Complex targets provide more practice with integrating and sequencing movement components, allowing children to extract more information about the underlying speech motor skill; complex targets also may subsume simpler movements which therefore receive practice as well. This hypothesis predicts a greater increase in perceptual speech accuracy at 1 week post treatment for children who receive Complex ASSIST than children who receive Simple ASSIST.

4.1.3.3 STUDY 3: WORD ASSIST VS. NONWORD ASSIST

Study 3 is a single-site Phase 1 randomized clinical trial using a prospective outcome-assessor-blinded two-arm group design. The critical outcome assessment point is 1-week post treatment (either T2 or T3, depending on the Immediate or Delayed allocation).

Word ASSIST involves ASSIST (see above) in which the targets are real words, selected based on personal functional relevance. Nonword ASSIST involves ASSIST in which the targets are nonwords, created by changing a stressed vowel and 0 or more other sounds in the personally relevant real words.

Word Hypothesis: Children with CAS learn more effectively with existing words than with nonwords. Real words enhance motivation due to their communicative relevance; real words may also receive practice outside the treatment setting. This hypothesis predicts a greater increase in perceptual speech accuracy at 1 week post treatment for children who receive Word ASSIST than children who receive Nonword ASSIST.

Nonword Hypothesis: Children with CAS learn more effectively with nonwords. Nonwords require activating and assembling novel motor plans, instead of relying on retrieving pre-existing, possibly incorrect speech motor plans and semantic activation; nonwords also allow for more systematic and controlled variation of phonetic context. This hypothesis predicts a greater increase in perceptual speech accuracy at 1 week post treatment for children who receive Nonword ASSIST than children who receive Word ASSIST.

4.1.3.4 STUDY 4: MASSED ASSIST VS. DISTRIBUTED ASSIST

Study 4 is a single-site Phase 1 randomized clinical trial using an outcome-assessor-blinded two-arm group design. The critical outcome assessment point is at T3.

Randomization involves permuted block-randomization with a block size of 4 to ensure equal sample sizes. Two of the block elements will indicate assignment to Distributed ASSIST (see *Section 1.2, Schema*). Children are allocated with equal probability to one of four groups (Immediate Massed, Delayed Massed, Distributed 1, Distributed 2) (5:5:5:5).

ASSIST is as above (complexity and lexicality to be determined by optimal outcomes in Studies 2 and 3) but delivered either over 2 weeks (Massed) or 4 weeks (Distributed).

Distributed Hypothesis: Children with CAS learn more effectively with distributed than with massed treatment. Distributed practice results in more forgetting, and requires more, deeper processing for the next attempt (reconstructing the movement from scratch), resulting in more detailed movement plans. This hypothesis predicts a greater increase in perceptual speech accuracy at 1 week post treatment for children who receive Nonword ASSIST than children who receive Word ASSIST

Massed Hypothesis: Children with CAS learn more effectively with massed than with distributed treatment. Massed practice facilitates neuroplastic processes (e.g., synaptogenesis) which in turn support sustained behavioral performance improvements (i.e. learning). This hypothesis predicts a greater increase in perceptual speech accuracy at 1 week post treatment for children who receive Nonword ASSIST than children who receive Word ASSIST.

4.2 SCIENTIFIC RATIONALE FOR STUDY DESIGN

This study design was selected for several reasons.

First, to establish experimental control against a no-treatment condition (the Delayed ASSIST group). As a first examination of ASSIST, a Phase 1 study against a no-treatment comparison is appropriate to establish that the intervention is better than absence of intervention.

Second, to enable examination of effects on distal outcome measures, which requires a group comparison design (vs. a within-participant or within-group design). As one of the first studies of CAS treatment to consider such distal outcomes (e.g., caregiver-rated communicative function), a group design is appropriate to evaluate distal effects and generate effect size data to power future trials on more meaningful distal outcome measures.

Third, randomizing children to different conditions (Complexity, Lexicality) within the Immediate and Delayed groups (using the same basic design and same procedures in Cycles 1 and 2) enables efficient evaluation of the “How” of ASSIST (procedures, techniques) and the “What” of ASSIST (targets). This yields both an assessment of the robustness of ASSIST (effect across conditions) and information to inform optimal parameters of ASSIST.

Fourth, to mitigate ethical concerns about withholding treatment from some children. By using a delayed control group design, all children receive the 16 hours of ASSIST, with the only difference in whether they receive ASSIST in the first or second two-week period.

Fifth, the intensive intervention period and study design facilitate recruitment and retention and a representative sample by lowering barriers to participation, and is also motivated by evidence suggesting intensive intervention is more effective for children with CAS.

4.3 JUSTIFICATION FOR INTERVENTION

CAS affects speech communication and thus participation in life, because virtually all social activities depend on speech communication. Children with CAS are at elevated risk for reading and academic challenges, reduced communicative participation, and reduced psychosocial well-being. These effects are long-term. Treatment progress is often slow for CAS, and intensive motor-focused treatment is recommended. Effective treatment for CAS has the potential to improve not only speech communication but also more distal outcomes, such as communicative participation.

ASSIST is delivered over 32 sessions for a total of 16 hours over 4 weeks (Study 4, Distributed group) or 2 weeks (all other groups). The amount is comparable to previous studies with other treatment approaches. ASSIST is delivered individually in a pull-out model in the context of a day camp setting. This context was chosen to minimize missed sessions and to provide a naturalistic supportive social environment. If at least 14 sessions (7 hours) are available, data are evaluable. All data are valuable given the current lack of RCT level evidence for integral stimulation treatments for CAS.

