4.4 END-OF-STUDY DEFINITION

Children are considered to have completed the study if they have completed the evaluation, baseline assessment (T1), at least 14 intervention sessions, and Week 4 (T2) and Week 7 (T3) assessments.

The end of the study is defined as completion by all children of the Week 7 (T3) assessments shown in the Schedule of Activities (SOA), **Section 1.3.**

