9.3 POPULATIONS FOR ANALYSES

Modified Intention-to-Treat (ITT) analysis will be used to statistically analyze the results (i.e., all randomized participants who received at least one session of the intended ASSIST intervention). Per-Protocol analysis will be used in the event that a participant changes intervention condition.

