9.4.2 ANALYSIS OF THE PRIMARY ENDPOINT(S)

The primary endpoint measure is change score from 1 week pre to 1 week post treatment for the populations described above in **Section 9.3, Populations for Analyses**. For perceptual accuracy, at least two independent data analysts (blinded to timepoint, treatment status, condition, and targets) score each target on an ordinal 3-point scale. Mean across the data analysts for each target is then used to compute the mean across treated targets (primary endpoint) and across the full 30-item target set (secondary endpoint 1) for each timepoint (T1, T2, T3). Means are converted to percentage accuracy by dividing means by 2. Finally, difference scores are then computed by subtracting the relevant pre-treatment timepoint from the relevant post-treatment timepoint. These change scores are the primary endpoint variable entered into the analyses described below and will be reported as means with standard error.

To address the effect of ASSIST (the *ASSIST Hypothesis*, Study 1), independent two-sample t-tests will be used to compare change scores (T2 – T1) between the Immediate ASSIST group and the No ASSIST delayed control group (combined sample across Cycles 1 and 2). A separate linear model will be fitted by adjusting for potential effect of study (Cycle 1/Cycle 2) to re-assess the initial efficacy of ASSIST.

To address the effect of complexity (*Simplicity vs. Complexity Hypothesis*, Study 2), independent two-sample t-tests will be used to compare change scores between conditions (i.e., Simple/Complex). Change scores will be based on T2 – T1 for the Immediate ASSIST group and T3 – T2 for the Delayed ASSIST group. Separate linear models will be fitted by adjusting for potential effect of ASSIST delivery time (Immediate/Delayed) to re-assess the effect of complexity.

To address the effect of lexicity (*Word vs. Nonword Hypothesis*, Study 3), independent two-sample t-tests will be used to compare change scores between conditions (i.e., Word/Nonword). Change scores will be based on T2 – T1 for the Immediate ASSIST group and T3 – T2 for the Delayed ASSIST group. Separate linear models will be fitted by adjusting for potential effect of ASSIST delivery time (Immediate/Delayed) to re-assess the effect of lexicity.

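### The 14-session mark for evaluable data (Protocol 4.3, 4.4) and the one-session analysis population (9.3) are not reconciled, and in Study 1 both depend on sessions that the two arms receive at different times.

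*Protocol*

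**What the plan says.** Protocol Section 4.3 gives the full course ("ASSIST is delivered over 32 sessions for a total of 16 hours") and then states: "If at least 14 sessions (7 hours) are available, data are evaluable". The next sentence reads: "All data are valuable given the current lack of RCT level evidence for integral stimulation treatments for CAS". Section 4.4 counts a child as having completed the study after screening, T1, "at least 14 intervention sessions, and Week 4 (T2) and Week 7 (T3) assessments".

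Section 9.3 defines a modified intention-to-treat set by a different count: "all randomized participants who received at least one session of the intended ASSIST intervention". Its only other population is triggered by something else: "Per-Protocol analysis will be used in the event that a participant changes intervention condition".

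Section 9.4.2 computes the primary change score "for the populations described above in" Section 9.3. For Study 1 it compares "change scores (T2 – T1) between the Immediate ASSIST group and the No ASSIST delayed control group". By the schema in Section 1.2, Immediate children are treated in weeks 2-3, before T2, and Delayed children in weeks 5-6, after T2.

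Section 7.2.1 keeps children who stop ASSIST in the study for the remaining procedures, and Section 5.5.2 asks families who withdraw to return for post-testing. The SAP defines no analysis population and mentions neither evaluability nor a session count.

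**The concern.** A child with 1 to 13 sessions and full T1, T2 and T3 data is in the analysis set under 9.3, is not a completer under 4.4, and does not meet the condition in 4.3. Because outcomes are still sought after treatment stops, such children can exist. The documents never say what *evaluable* means for the analysis, so someone preparing the data set could apply either threshold after seeing the data.

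In Study 1 the choice is not neutral between arms. Sessions accumulate before the T2 outcome in the Immediate arm only. A session threshold could therefore take out Immediate children who stopped early for reasons related to progress, while similar children in the Delayed arm stay because they have not yet had the chance to stop. The one-session minimum in 9.3 shares the defect in a milder form: a Delayed child whose T2 − T1 change is already observed leaves Study 1 by not starting in week 5.

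Section 9.2 says the trial is meant to supply effect sizes for later trials, so an inflated estimate would carry into their sample sizes.

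**Working it through.** **1. Inputs from the documents.** 32 sessions planned; thresholds of 14 (4.3, 4.4) and 1 (9.3); four sessions per day on the 2-week schedule and two per day in the Distributed group (6.1.1.1.1); Study 1 with 20 per arm, effect size 0.909, two-sided alpha 0.05, two-sample t-test (9.2).

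**2. The plan's own figure.** Exact power from the noncentral t with df = n1 + n2 − 2 and noncentrality d × √(n1·n2/(n1 + n2)). At 20 per arm the noncentrality is 0.909 × √10 = 2.87.

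| n per group | 20 | 19 | 18 | 17 | 16 | 15 |
|---|---|---|---|---|---|---|
| Table 2 | 80% | 77% | 75% | 72% | 70% | 67% |
| Recomputed | 80.0% | 77.8% | 75.5% | 72.9% | 70.1% | 67.1% |

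Table 2 reproduces.

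**3. The two thresholds.** 14/32 = 43.75% of the planned course; 1/32 = 3.1%. On the 2-week schedule, 14/4 = 3.5 treatment days, so a child who stops after day 3 has 12 sessions and falls between the rules. In Study 4 the same count is 3.5 days for Massed and 14/2 = 7 days for Distributed, so it does not mean the same thing in the two groups.

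**4. Who can fall short before T2.** Immediate: 0 to 32 sessions by T2. Delayed: 0 by design. A Delayed child could fail a 14-session filter only by other routes: low attendance in weeks 5-6, after the T2 outcome, or a family that stops before T2 and returns only for testing.

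**5. Power if k Immediate children and no controls are removed** (d = 0.909): k = 1, 78.9%; k = 2, 77.7%; k = 3, 76.4%. The loss is small. The issue is bias.

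**6. Inflation of the effect.** Assume 0.909 is the effect over all randomised children and the SD is unchanged.
- If the removed children gain no more than controls, the remaining effect is 0.909 × 20/(20 − k): 0.957, 1.010 and 1.069 for k = 1, 2, 3 (+5%, +11%, +18%).
- If they obtain 12/32 of the full effect (an assumption: benefit proportional to 12 sessions), the factor is 20/(20 − 0.625k): +3%, +7%, +10%.
- Required sample size varies roughly as 1/d². In the first case a later trial sized on the inflated effect would have (19/20)² = 90%, (18/20)² = 81% or (17/20)² = 72% of the children it needs.

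**7. Type I error with no true effect** (simulation, 20,000 runs, 20 per arm, normal data, removal from the Immediate arm only).

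| Assumed selection | Type I error |
|---|---|
| 10-20% low attenders, gaining 0.5-1.0 SD less | 5.1% to 8.2% |
| k = 1, 2, 3 removed on a variable correlated 0.5 with gain | 5.3%, 6.4%, 7.2% |
| Exactly the lowest k = 1, 2, 3 gainers removed | 6.9%, 10.4%, 14.5% |

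In the first scenario the treated-arm bias is 0.05 to 0.20 SD, and keeping every child gives 4.8% to 5.1%.

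**The case against.** A reader might infer that 4.3 contradicts 9.3, that only data from 14 sessions upward count, and that the Study 1 estimate is therefore biased upward. The documents do not support that. Section 4.3 states a sufficient condition; it does not say that fewer sessions exclude a child, and the sentence after it values all data. Section 4.4 defines completion, and a completer definition commonly differs from an analysis set. Section 9.4.2 sends the primary analysis to 9.3, 9.4.3 follows it for secondary endpoints, and the per-protocol trigger is a change of condition. Section 6.4 logs absences so that the amount of treatment can be adjusted for, which points towards keeping partial-course children. All of this stands.

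A reader might also infer that only treated children could ever be removed. That is too strong: Delayed children have the other routes in step 4 of the working. Nor is the asymmetry peculiar to 14 sessions, since the one-session rule has it too.

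The frustration route is narrower than it looks. Section 7.1 raises possible withdrawal after more than three consecutive treatment days of high scores, hence day 4 at the earliest. A fully attending child on the 2-week schedule then has 4 × 4 = 16 sessions, above the mark. Falling below 14 in Study 1 needs absences or an earlier stop, and Section 7.2.2 expects few withdrawals. On the two-per-day schedule the same day gives 4 × 2 = 8 sessions, below the mark, so in Study 4 the count could depend on the assigned condition.

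What remains is that a numerical mark for evaluable data serves little purpose unless data below it are treated differently. Section 10.1.2 also lists insufficiently evaluable data as a ground for discontinuing the study. The term's role in the analysis should not be left to be settled later.

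**Conclusion.** The concern holds as an unreconciled definition, not as a stated exclusion rule or a demonstrated bias. Two session thresholds, 14 and 1, stand in the protocol with no passage relating them, and the SAP is silent. Any bias arises only if *evaluable* is applied as a filter, or through the milder route in 9.3 of dropping a Delayed child who never starts.

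The size is conditional, because the documents give neither a low-attendance rate nor gains by attendance. For 1 to 3 of 20 Immediate children removed, inflation is 5% to 18% if they gain no more than controls and 3% to 10% if they gain 12/32 of the effect. Type I error is about 5% to 8% under moderate selection. The 10% to 15% range is a worst case that requires the 2 or 3 lowest gainers to be exactly the children removed.

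Adopting 9.3 as it stands would settle which threshold applies but would leave the Study 1 asymmetry in place.

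**What to change.** - **Sections 4.3 and 4.4:** state that 14 sessions is a descriptive label for treatment completion and does not determine who is analysed.
- **Section 9.3, Study 1:** analyse all randomised children with T1 and T2 data in their randomised arm, whatever number of sessions they received, including none.
- **Section 9.3, Studies 2-4:** analyse all randomised children with the relevant pre and post data in their assigned condition, on the same terms.
- **Sensitivity:** report any one-session or 14-session set only as a labelled sensitivity analysis, with the number removed per arm.
- **SAP:** repeat the population definition, since it has none.

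The 9.3 change has to drop the one-session minimum for the main analysis. Otherwise a child with no sessions but with T1 and T2 data would remain excluded.

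The cost is wording in three protocol sections and one SAP sentence, with no extra data collection. The downside is a slightly smaller estimated effect if some children receive little treatment.
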